#### DUX4 COMPOSITE SCORE

Missing composite score will be imputed by three methods as follows

1. Mean Imputation: For subjects missing “pre”, impute using the MEAN(pre) of non-missing subjects. For subjects missing “post”, impute using MEAN(post) from non-missing subjects.
2. Worst case imputation: For subjects missing “pre”, impute using MIN(pre) of non-missing subjects. For subjects missing “post”, impute using MAX(post) from non-missing subjects.

---

3. Median Imputation: For subjects missing “pre”, impute using the MEDIAN(pre) of non-missing subjects. For subjects missing “post”, impute using MEDIAN(post) from non-missing subjects.

### 2.3.7 Other Data Points Definition

NA

## 2.4 MULTIPLE COMPARISONS/MULTIPLICITY

No formal statistical tests will be employed in the study, therefore there is no multiplicity adjustment for type I error to be made.

## 2.5 EXAMINATION OF SUBGROUPS

Depending on the number of subjects in each sub-category, subgroup analyses may be conducted on [REDACTED]

## 3 STATISTICAL ANALYSES

### 3.1 SUBJECT INFORMATION

Unless indicated otherwise, the results for subject information will be based on the safety analysis set.

#### 3.1.1 Disposition of Subjects

The number of subjects screened and the number (percent) of subjects who failed screening will be summarized.

Study Completion: The number (percent) of treated subjects who completed the study (Week 60) and who discontinued from the study will be summarized according to the reasons for discontinuation.

Entered Study Extension: The number (percent) of treated subjects who entered the extension of the study.

#### 3.1.2 Protocol Deviations

The number and percentage of subjects with significant protocol deviations will be presented in a summary table. Line listings of all collected protocol deviations will also be presented.

#### 3.1.3 Demographics and Baseline Characteristics

Demographic and baseline characteristics will be summarized. The continuous variables will be summarized using descriptive statistics (n, mean, standard deviation [SD], median

and range [minimum and maximum]). The minimum and maximum observations will be presented to the same number of decimal places as the original data. The mean and median will be rounded to one more decimal place than the original data, while the SD will be to two more decimal places. The categorical variables will be summarized by absolute and relative frequencies. There are no formal hypotheses regarding baseline demographics and characteristics, hence no p-values will be provided.

Continuous demographic and baseline variables include age (years), baseline weight (kg), body mass index (BMI) in kg/m^2, etc. Categorical variables include sex (male, female, undifferentiated), race (White, Black or other), age group (18 to < 50 years, >=50 to <= 65 years, Ethnicity (Hispanic or Latino, not Hispanic or Latino), etc.

The status of the disease at screening will be summarized according to his/her age at diagnosis, number of FSHD repeats, Ricci score, and family history of FSHD. Subject's age at diagnosis will be summarized as a continuous variable and as a categorical variable, with categories of <18, ≥18 to < 50 years, and ≥ 50 to <= 65 years.

#### **3.1.4 Medical History**

Medical History will be coded using the Medical Dictionary for Regulatory Activities (MedDRA), version 23.0. The number of subjects and their percentages reporting a history of any medical condition will be summarized by System Organ Class (SOC) and preferred term (PT). A subject data listing of medical and surgical history will be provided.

#### **3.1.5 Prior and Concomitant Therapy**

All investigator terms for medications will be coded using the World Health Organization (WHO) Drug Dictionary (Global B3, March 2019). The number (percent) of subjects who took prior and concomitant medications will be summarized using Anatomical Therapeutic Chemical (ATC) Classification, and WHO Drug preferred term.

Prior medications will be defined as medications that started before the first dose of study drug, regardless of when the medication ended. Concomitant medications will be defined as medications continued or newly received on or after the first dose date of study drug, up to 7 days following the last dose. A given medication can be prior, concomitant, or both.

#### **3.1.6 Treatment Compliance**

Descriptive summary statistics will be provided for time on treatment and compliance for all patients.

Mean, standard deviation, median, minimum, and maximum amount of study drug returned will be provided. The cell frequencies and percentage of patients in each category (<80%, >=80%) will be provided. Compliance for the main study will be calculated as (actual dose/planned dose)\*100 where planned dose is 7.5 mg\*2\*2\*total duration of treatment. Compliance for the study extension will be calculated as (actual dose/planned dose)\*100 where planned dose is 7.5 mg\*2\*2\*total duration of treatment when 2 tablets were given plus 15 mg\*2\*total duration of treatment when 1 tablet was given.

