### **3.1.5 Treatment Duration**

The total duration for this study will be approximately 68 weeks, and the total treatment duration will be approximately 52 weeks in the main portion of the study. Subjects will have the option of participating in the extension portion of the study until 90 days after commercial drug is available post regulatory approval or study termination.

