## **8.5 Withdrawal of Individual Subjects**

### **8.5.1 Study Drug Interruption or Discontinuation**

Before trial medication is administered, changes in the subject's health status since the previous visit must be checked, including laboratory results if applicable. The investigator must temporally interrupt or permanently discontinue the study drug if continued administration of the study drug is believed to be contrary to the best interests of the subject. The interruption, lowering (to mg PO BID), or premature discontinuation of the study drug might be triggered by an AE, a diagnostic or therapeutic procedure, an abnormal assessment (eg, ECG or laboratory abnormalities), or, for administrative reasons, the withdrawal of the subject's consent. The reason for study drug interruption, dose lowering either transiently or permanently, or premature discontinuation must be clearly documented and approved by the sponsor.

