### 3.2.1 Extent of Exposure

Descriptive summary statistics will be provided for time on treatment.

Time on treatment in days will be derived using the following formula:

Time on treatment (days) = (date of last dose) – (date of first dose) + 1If the last dose date is missing, or if a subject is lost to follow-up, and the drug accountability log confirms that the subject has taken the study drug, the visit date following the last completed drug accountability log will be used.

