### 3.2.2.1 Deaths, Serious and Other Significant Adverse Events

The number of subjects and their percentages with TEAEs leading to death will be summarized by MedDRA SOC and PT. A subject data listing of all AEs leading to death will be provided.

Note: A summary table will not be provided if there are no deaths in the study.

The number of subjects and their percentages with treatment-emergent SAEs will be summarized by MedDRA SOC and PT. A subject data listing of all SAEs will be provided.

The number of subjects and their percentages with TEAEs leading to discontinuation from study treatment will be summarized by MedDRA SOC and PT. A subject data listing of all AEs leading to discontinuation from study treatment will be provided.

The number of subjects and their percentages with TEAEs and the relation to study treatment will be summarized by MedDRA SOC and PT.

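### SAP 3.1.6 measures compliance against full dose throughout, so authorised interruption or dose lowering looks like missed doses, and no summary shows adverse events that led to either

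*SAP*

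**What the plan says.** Protocol 8.5.1 allows the study drug to be interrupted, lowered or stopped, and names an adverse event among the possible triggers. These are authorised changes: "The reason for study drug interruption, dose lowering either transiently or permanently, or premature discontinuation must be clearly documented and approved by the sponsor".

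SAP 3.1.6 gives the compliance ratio: "Compliance for the main study will be calculated as (actual dose/planned dose"). For the main study, "planned dose is 7.5 mg" times two tablets, times two intakes a day, times total duration of treatment. For the extension, the planned dose is split by tablet strength: "total duration of treatment when 2 tablets were given plus 15 mg" twice daily for the time on one tablet. The result is also categorised: "The cell frequencies and percentage of patients in each category (<80%, >=80%) will be provided".

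SAP 3.2.1 covers exposure with a single measure: "Descriptive summary statistics will be provided for time on treatment". That time is the last dose date minus the first dose date plus one day, with no deduction for gaps.

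Among actions taken on study drug because of an adverse event, SAP 3.2.2.1 summarises one: "The number of subjects and their percentages with TEAEs leading to discontinuation from study treatment will be summarized by MedDRA SOC and PT". Protocol 10.2.3 likewise singles out only TEAEs leading to discontinuation, as a listing.

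**The concern.** A compliance percentage is normally read as the extent to which subjects took what they were told to take. Here the denominator is the full protocol dose, whatever the investigator had prescribed. A subject whose drug was lowered for an adverse event, with sponsor approval, and who then took every tablet as instructed gets the same kind of score as a subject who skipped doses. Under one reading of the formula, the same applies to an authorised interruption.

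No other planned summary separates the two cases. Time on treatment includes gap days, and the only drug action summarised for TEAEs is discontinuation.

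Safety and tolerability form the primary objective of both the main study and the extension. In a single-arm, long-term study, the need to interrupt or lower the drug because of an adverse event is direct evidence on tolerability. The plan collects the reason but provides no summary of it.

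**Working it through.** The plan states no expected compliance figure, so there is none to reproduce. The check applies the SAP formula to subjects who take every dose prescribed to them.

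**Inputs**
- Daily planned dose (SAP 3.1.6): 7.5 × 2 × 2 = 30 mg on two tablets, or 15 × 2 = 30 mg on one. Both equal the 15 mg twice daily of Protocol 6.6, so the extension formula adjusts for tablet strength and nothing else.
- Duration D: Protocol 3.1.5 says "the total treatment duration will be approximately 52 weeks in the main portion of the study". I take D = 52 × 7 = 364 days, giving a planned total of 30 × 364 = 10,920 mg.
- Cut-off: 80% (SAP 3.1.6).
- Subjects: 14 enrolled (Protocol 4.1).
- Length and frequency of interruptions: not given, so a range is shown.
- Lowered dose level: not legible in Protocol 8.5.1. The fractions below are arithmetic illustrations, not proposed doses.

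**Interruption of g days, D running from first to last dose**

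Compliance = 100 × 30(D − g) / (30 × D) = 100 × (364 − g)/364.

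| Gap (days) | Compliance | Class |
|---|---|---|
| 14 | 96.2% | ≥80% |
| 28 | 92.3% | ≥80% |
| 56 | 84.6% | ≥80% |
| 72 | 80.2% | ≥80% |
| 73 | 79.9% | <80% |
| 84 | 76.9% | <80% |

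The score drops below 80% when g exceeds 0.2 × 364 = 72.8 days. In every row, time on treatment under SAP 3.2.1 still reads 364 days. If the subject takes an assumed 90% of doses on the remaining days, the condition is 0.9 × (364 − g)/364 < 0.8. That gives g > 364 × (1 − 0.8/0.9) = 40.4, so 41 days.

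**Interruption, D excluding gap days**

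The gap leaves both numerator and denominator, and the score is 100%.

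**Lowering to a fraction f of full dose for L days (either reading of D)**

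Compliance = 100 × [(364 − L) + f × L]/364, which is below 100% for any f < 1 and L > 0. It falls below 80% when L > 72.8/(1 − f).

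| Assumed f | First L with score <80% |
|---|---|
| 0.25 | 98 days |
| 0.50 | 146 days |
| 0.75 | 292 days |

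At f = 0.5, periods of 84, 168 and 364 days give 88.5%, 76.9% and 50.0%.

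**Permanent discontinuation**

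A stop at day 100 with all doses taken gives 100 × (30 × 100)/(30 × 100) = 100%, because the span ends at the last dose. Early stopping does not lower the score, whereas continuing on a lowered dose does.

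**Weight of one subject**

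1/14 = 7.1 percentage points in the category table.

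**The case against.** The strongest counter-argument is that little depends on this number. Compliance sits under subject information in the SAP, outside the primary-endpoint analyses. The primary endpoint is built on adverse events, laboratory results, ECGs and vital signs. There is one analysis set (at least one dose), no per-protocol set, and no exclusion by compliance. The SAP does not label the lower class as non-compliant. All of this stands, and it limits the consequences.

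A reader might infer that intolerance managed by interruption or lowering would appear nowhere as a tolerability event. The documents do not support that. The triggering event is a TEAE, counted by SOC and PT, by maximum severity and by relation to treatment, and every adverse event is listed. What is missing is the link to the drug action.

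A reader might also infer that any such subject falls in the lower compliance class. That is true only of long gaps or sustained lowering, as the tables show.

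Next, total duration of treatment is undefined in 3.1.6, and the extension wording about when tablets were given could mean periods on drug only. This also stands: the interruption result depends on the first-to-last-dose reading. That reading is plausible, because 3.2.1 holds the only duration the SAP defines and 3.1.6 reports time on treatment beside compliance, but it is not certain. The lowering result does not depend on it.

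Finally, actual over full planned dose is a legitimate quantity, and long time on treatment beside a low percentage does reveal a dose shortfall. Replacing it with a prescribed-dose ratio alone would hide that shortfall. This is right, and it is why the full-dose ratio should be kept under its proper name, dose intensity. It does not show whether a shortfall was ordered or was missed doses.

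**Conclusion.** The point holds in a limited form and is worth correcting. For any dose lowering, the 3.1.6 formula scores a fully adherent subject below 100%, on either reading of duration. For interruption it does so if duration runs from first to last dose. On that reading and an assumed 364-day course, the 80% line is crossed only from 73 gap days, with full adherence otherwise. Shorter authorised gaps lower the mean without changing the category.

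The documents do not say how many subjects were interrupted or lowered, so the practical effect is unknown; it could be nil. Each subject who changes class moves the category by 7.1 points.

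Two gaps do not depend on the compliance formula: time on treatment in 3.2.1 includes interruption days, and no summary shows TEAEs that led to interruption or lowering. It would be too strong to say that the plan misreports its primary endpoint or loses the adverse event.

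**What to change.** - **SAP 3.1.6:** for compliance, define planned dose as the dose prescribed on each day, set to zero on documented, investigator-directed interruption days. State what total duration of treatment means. A subject who takes every prescribed dose then scores 100% in all the scenarios above.
- **SAP 3.1.6 or 3.2.1:** report actual dose over full protocol dose separately, labelled dose intensity, so that the shortfall stays visible.
- **SAP 3.2.1:** also report time on treatment excluding documented interruption days.
- **SAP 3.2.2.1:** add the number and percentage of subjects with TEAEs leading to interruption, and with TEAEs leading to dose lowering, by SOC and PT.

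The cost is SAP wording and two short extra tables. The reasons are already required by Protocol 8.5.1; I assume that the dates and the prescribed dose were recorded with them. Nothing here proposes a dose level or a rule for when to interrupt or lower.

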## 3.2 ANALYSIS FOR PRIMARY ENDPOINTS

Safety variables include treatment-emergent adverse events (TEAEs), serious adverse events (SAEs), clinical laboratory parameters, vital signs, 12-lead electrocardiogram (ECG) results, and extent of exposure. Study Day 1 for all safety analyses is defined as the date of the first dose of study drug.

### 3.2.1 Extent of Exposure

Descriptive summary statistics will be provided for time on treatment.

Time on treatment in days will be derived using the following formula:

Time on treatment (days) = (date of last dose) – (date of first dose) + 1If the last dose date is missing, or if a subject is lost to follow-up, and the drug accountability log confirms that the subject has taken the study drug, the visit date following the last completed drug accountability log will be used.

### 3.2.2 Adverse Events (AEs)

The AE verbatim descriptions (investigator terms from the case report forms [CRF]) will be classified into medical terminology using the Medical Dictionary for Regulatory Activities (MedDRA). AEs will be coded to primary System Organ Class (SOC) and preferred term (PT) using MedDRA, version 23.0.

A TEAE is defined as an AE that meets any of the following conditions:

- begins on or after the first dose of study drug and before the stop of study drug + 7 days;
- begins before the first dose of study drug and worsens on or after the first dose of study drug and before the stop of study drug + 7 days;
- is completely missing an onset date and an end date;

- is completely missing an onset date and the end date is on or after the first dose of study drug.

Only those AEs that are treatment emergent will be included in summary tables. All AEs, treatment emergent or otherwise, will be presented in subject data listings.

In summary tables, the incidence of TEAEs will be reported as the number of subjects and their percentages with TEAEs within SOC and PT. Subjects will be counted only once within a SOC and PT, even if the subject experienced more than one TEAE within a specific SOC and PT. The number of subjects and their percentages with TEAEs will also be summarized by maximum severity (mild, moderate, or severe) (or by highest common terminology criteria for AEs [CTCAE] grade).

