### 3.1.1 Study Design Schema

Abbreviations: 6-MWT=6-minute walking test; D=day; COAs=clinical outcome assessments; DUX4=double homeobox 4; FSHD-HI=facioscapulohumeral muscular dystrophy-Health Index; FSHD-RODS=FSHD-Rasch-built Overall Disability Scale; MFM=Motor Function Measure; MRI=magnetic resonance imaging; PGIC=Patients' Global Impression of Change; PK=pharmacokinetics; PRO=patient-reported outcome; QMT=quantitative myometry; RWS=Reachable Workspace; TUG=Timed Up and Go; W=week.

Only subjects terminating the study after Week 60 will have the Visit 10 End of Study visit. Subjects proceeding to the extension will continue to Week 72 visit.

Note: All visits during the extension will have a  $\pm$  4-week window; early termination visits can occur at any time.

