### **Adverse Events**

AEs will be coded using the Medical Dictionary for Regulatory Activities (MedDRA). The overall incidence of AEs will be summarised by MedDRA primary System Organ Class (SOC) and Preferred Term (PT).

All AEs will be displayed in listings or graphs when appropriate. In addition, SAEs and treatment-emergent AEs (TEAEs) leading to discontinuation of study drug will be listed.

A TEAE is defined as an AE observed after starting administration of the specific treatment. If a subject does experience an event both prior to and after starting administration of a treatment, the event will be considered a TEAE (of the treatment) only if it has worsened in severity (ie, it is reported with a new start date) after starting administration of the specific treatment and prior to the start of another treatment.

The number of TEAEs and the number of subjects with at least 1 TEAE will be summarised for the following:

- SOC and PT;
- SOC, PT, and maximum severity;
- SOC, PT, and maximum drug relatedness.

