### 2.3.5 Analysis Visit Windows

The following non-overlapping visit windows will be used to assign data to visits for data analyses:

Table 1 Visit windows for measurements

Adjusted Defined Windows Visit	Scheduled Study Day	Maximum Windows
Baseline Visit (First dose/Day 1)	Day 1	<= Day 1
Week 4 post-treatment	Day 28	>Day 1 to <=Day 42
Week 8 post-treatment	Day 56	>Day 42 to <=Day 98
Week 20 post-treatment	Day 140	>Day 98 to <=Day 182
Week 32 post-treatment	Day 224	>Day 182 to <=Day 266
Week 44 post-treatment	Day 308	>Day 266 to <=Day 350
Week 56 post-treatment	Day 392	>Day 350 to <=Day 406
60 Weeks post-treatment (EOS, Protocol Visit 10)	Day 420	>Day 406
64 Weeks post-treatment (Protocol Week 72)	Day 448	>Day 406 to <=490

Adjusted Defined Windows Visit	Scheduled Study Day	Maximum Windows
76 Weeks post-treatment (Protocol Week 84)	Day 532	>Day 490 to <=Day 574
88 Weeks post-treatment (Protocol Week 96)	Day 616	>Day 574 to <=Day 658
100 Weeks post-treatment (Protocol Week 108)	Day 700	>Day 658 to <=Day 742
112 Weeks post-treatment (Protocol Week 120)	Day 784	>Day 742 to <=Day 826
124 Weeks post-treatment (Protocol Week 132)	Day 868	>Day 826 to <=Day 952
148 Weeks post-treatment (Protocol Week 156)	Day 1036	>Day 952 to <=Day 1120
172 Weeks post-treatment (Protocol Week 180)	Day 1204	>Day 1120 to <=Day 1288
196 Weeks post-treatment (Protocol Week 204)	Day 1372	>Day 1288 to <=Day 1456
220 Weeks post-treatment (Protocol Week 228)	Day 1540	>Day 1456 to <=Day 1624
244 Weeks post-treatment (Protocol Week 252)	Day 1708	>Day 1624 to <=Day 1792
268 Weeks post-treatment (Protocol Week 276)	Day 1876	>Day 1792 to <=Day 1960

Only subjects terminating the study after Week 56 post-treatment will have the Week 60 follow-up (EOS) visit. Subjects proceeding to the extension will continue to 64 Weeks post-treatment (protocol week 72) visit. Subjects will remain in the extension until 90 days after commercial drug is available post regulatory approval or until the study is discontinued by the sponsor. During the extension, subjects will attend clinic visits approximately every 24 weeks. All subjects who complete or discontinue from treatment will complete a safety follow-up visit 7 days ( $\pm 3$  days) after the last dose of study drug.

If multiple visits are recorded in the same analysis window, the later visit will be used in the analysis.

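### The SAP's treatment-emergent window closes before day 7 after the last dose, so adverse events that start later are collected but appear in no AE summary table

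*SAP*

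**What the plan says.** SAP 3.2.2 defines a treatment-emergent adverse event (TEAE) by date. A new event qualifies if it "begins on or after the first dose of study drug and before the stop of study drug + 7 days". A pre-existing event qualifies if it "worsens on or after the first dose of study drug and before the stop of study drug + 7 days". Events without an onset date have their own rules; one of them keeps an event that "is completely missing an onset date and the end date is on or after the first dose of study drug".

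The same section then says: "Only those AEs that are treatment emergent will be included in summary tables". SAP 3.2.2.1 builds the tables for deaths, SAEs, discontinuations and relatedness on TEAEs as well. Nothing is lost from the listings: "All AEs, treatment emergent or otherwise, will be presented in subject data listings".

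On follow-up, SAP 2.3.5 and protocol 3.1.4 agree: "All subjects who complete or discontinue from treatment will complete a safety follow-up visit 7 days" after the last dose, with a margin of 3 days either way. Protocol 3.1.3 places Visit 10, the main-study end-of-study visit, at Week 64 ± 2 weeks, and protocol 3.1.1 adds: "Only subjects terminating the study after Week 60 will have the Visit 10 End of Study visit". Protocol Table 2 has AEs collected to end of study; Table 3 has them collected through the safety follow-up visit.

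The protocol's own definition, in 10.2.3 under Adverse Events, is wider: "A TEAE is defined as an AE observed after starting administration of the specific treatment". That section also plans a summary of overall AE incidence by system organ class (SOC) and preferred term (PT).

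**The concern.** Safety and tolerability is the primary endpoint of both study parts, and for adverse events the result a reader will use is the incidence table. The follow-up visits exist to pick up events after dosing stops. A window that closes just short of the nominal follow-up day leaves part of what those visits collect out of every AE table. Because the SAP tabulates only TEAEs, no wider AE table catches the remainder, although the protocol planned one. The definition is also narrower than the protocol's, and SAP section 5, which lists changes to the planned analyses, does not mention it. With 14 subjects enrolled, one subject more or fewer is visible in any percentage.

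**Working it through.** The plan gives no figure to reproduce here, so this is a count of days. Take the last dose (the stop of study drug) as day 0.

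**Inputs**
- Window limit: onset or worsening strictly before day 7, so days 0 to 6 are in and day 7 onward is out (SAP 3.2.2).
- Safety follow-up visit: 7 ± 3 days, so days 4 to 10 (SAP 2.3.5, protocol 3.1.4).
- Visit 10: Week 64 ± 2 weeks (protocol 3.1.3). Last dose taken at the nominal Week 60, an assumption, since Visit 9 has its own window.
- Subjects: 14 (protocol 4.1).

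**Formula.** For a visit on day *v*, the onset days collected but outside the window number max(0, *v* − 6), out of *v* post-dose days.

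| Visit | Day *v* | Days in | Days out | Share out |
|---|---|---|---|---|
| Safety follow-up | 4, 5 or 6 | all | 0 | 0 |
| Safety follow-up, nominal | 7 | 6 | 1 | 1/7 = 14% |
| Safety follow-up | 8 | 6 | 2 | 2/8 = 25% |
| Safety follow-up | 9 | 6 | 3 | 3/9 = 33% |
| Safety follow-up, latest | 10 | 6 | 4 | 4/10 = 40% |
| Visit 10, earliest | 14 | 6 | 8 | 8/14 = 57% |
| Visit 10, nominal | (64 − 60) × 7 = 28 | 6 | 22 | 22/28 = 79% |
| Visit 10, latest | 42 | 6 | 36 | 36/42 = 86% |

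One subject is 1/14 = 7.1 percentage points of incidence.

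**Definitions side by side.** The protocol starts the TEAE period at first dose and sets no limit after the last dose. For worsening events it mentions the start of another treatment, which does not arise with a single study drug. The SAP adds the 7-day limit. The SAP's concomitant-medication window (3.1.5) runs up to 7 days after the last dose and reads as including day 7, so a medicine started on day 7 for a new event would be tabulated while the event would not.

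**Which tables are touched.** All AE tables carry the TEAE restriction. The discontinuation table should lose little in practice, because an event that causes a subject to stop drug normally starts before the stop. Laboratory, vital-sign and ECG summaries (SAP 3.2.3 and 3.2.4) carry no TEAE restriction, and Visit 10 has an analysis window in SAP Table 1.

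**Testing possible limits**
- Day 7 inclusive: follow-up visits on days 8, 9 and 10 still leave 1, 2 and 3 days out, and a nominal Visit 10 leaves 28 − 7 = 21.
- Day 10 inclusive: 0 days out for every visit from day 4 to day 10; 28 − 10 = 18 of 28 remain out at a nominal Visit 10.
- Visit 10 itself: 0 days out, but a subject who stops drug near Week 14 and stays on study would carry about 64 − 14 = 50 weeks off drug labelled treatment-emergent.

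**The case against.** A short tail after exposure is a legitimate way to define treatment-emergent. Seven days matches the nominal follow-up visit and roughly matches the concomitant-medication window, and protocol 10.1 leaves implementation detail to the SAP. No event is hidden: SAP 3.2.2.1 adds separate listings of all SAEs and of all AEs leading to death or discontinuation. In a 14-subject, single-arm, open-label pilot without hypothesis tests, a late SAE would be seen in a listing, and no decision rule depends on the TEAE count. All of this stands, and it limits how serious the point is. It does not explain why the nominal follow-up day falls outside the window, or why the narrowing goes unrecorded. A listing also gives no incidence.

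Three stronger readings are tempting and are not supported:
- A reader might infer that events found at the follow-up visits are left out as such. The rule uses the date of onset or worsening, not the visit of detection. An event starting on days 0 to 6 and reported at follow-up is tabulated, as are events that meet the missing-date rules. A follow-up visit on days 4 to 6 loses nothing.
- A reader might infer that every primary-endpoint summary is affected. Only the AE tables are.
- A reader might take 79% as the share of events lost, or assert a known bias. It is a share of calendar days for subjects who have Visit 10. The documents do not say how many of the 14 did not roll over, and give no post-dose AE rate.

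**Conclusion.** The concern holds in limited form. AEs with onset or worsening dated day 7 or later after the last dose are collected and listed but enter no AE incidence table. The gap is at most 4 onset days for a safety follow-up visit within its window. For a subject who ends at Visit 10 it is 22 of 28 days at nominal timing, and 8 of 14 to 36 of 42 across the Visit 10 window. These counts assume that the stop of study drug means the last dose, that *before* is applied strictly, and that the last dose falls at nominal Week 60.

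The direction is clear: omission can only leave tabulated incidence equal to or below incidence over the collected period. The amount cannot be sized; 7.1 points per omitted subject is a scale, not an estimate. The SAP departs from protocol 10.2.3 in two ways, the end limit and the loss of the overall AE incidence summary, and section 5 mentions neither. This is worth correcting because safety is the primary endpoint and the correction is cheap. It does not undermine the safety evaluation as a whole.

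**What to change.** 1. In SAP 3.2.2, for all subjects, define TEAEs as onset or worsening from first dose through last dose + 10 days inclusive, or through the safety follow-up visit (including a combined early-termination and follow-up visit, which protocol Table 3 allows without a stated latest day) if that is later. For this definition Visit 10 should not count as the safety follow-up visit.
2. Add one separate summary by SOC and PT of post-treatment AEs and SAEs with onset after that window through end of study. It covers the time up to Visit 10 and subjects who stop drug but stay on study, which protocol 8.5.2 permits, without labelling long off-drug periods treatment-emergent.
3. Record in SAP section 5 the departure from the protocol's TEAE definition and the dropped overall AE incidence summary. Protocol 10.1 requires deviations from planned analyses to be justified in the clinical study report.
4. Reconcile the follow-up timing: protocol 3.1.4 gives 7 ± 3 days after last dose for all subjects who complete or discontinue treatment, while 3.1.3 gives Week 64 ± 2 weeks for the main study. The documents should state which visits apply to a subject who does not roll over.

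The cost is a change of SAP wording, one date derivation and one extra table. The downside is that a few late, unrelated events will enter the tables.
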